6.2.2. Study drug preparation

A. ¹⁷⁷Lu–J591

The humanized monoclonal antibody–huJ591 is provided by [name]. Radionuclide conjugation will be done at the Division of Nuclear Medicine, Department of Radiology, Weill Cornell Medicine.

The DOTA–J591 antibody molecule is labeled with radiometal ¹⁷⁷Lu in 1.0 M ammonium acetate buffer at pH 7.0. The radiolabeled J591 complex is then purified using size–exclusion column chromatography. To avoid the effects of autoradiolysis on the antibody, reaction time is minimized and the radiolabeled antibody preparations are formulated in phosphate buffered saline containing not more than 1% Human Serum Albumin (HSA). All reagents used in the conjugation and purification of J591 are made with pyrogen–free water. Radiolabeled J591 is periodically tested for sterility and pyrogenicity.

Each patient dose will be supplied to the study site on the day of or day before treatment by the central radiopharmacy. The J591 mAb is a deimmunized monoclonal antibody directed at the

extracellular domain of human PSMA. For additional details, see Section 1. Radiolabeled antibody preparations are formulated in phosphate buffered saline containing not more than 1% Human Serum Albumin (HSA). In order to radiolabel J591 with β^- emitting radionuclides, the antibody molecule is first conjugated to a macrocyclic chelating agent, 1,4,7,10-tetraazacyclododecane- N,N',N'',N''' -tetraacetic acid (DOTA) by direct coupling of one of the four carboxylic acid groups of DOTA to the primary amines present in the protein structure. The radiolabeling of J591 with ^{177}Lu is achieved by adding the radionuclide to the ammonium acetate buffered J591. To avoid the effects of autoradiolysis on the antibody, reaction time is minimized and the reaction mixture is purified with a size exclusion column prior to administration. All reagents used in the conjugation and purification of J591 are made from pyrogen-free water. Radiolabeled J591 is tested periodically for sterility and pyrogenicity. Labeling efficiency and radiochemical purity will be determined using ITLC. Immunoreactivity of radiolabeled J591 mAb preparations will be determined using PSMA+ LNCaP tumor cells.

The material produced are subjected to quality assurance testing as outlined in the Food and Drug Administration "Points to Consider". All production data and supporting documents, together with the results of all quality assurance testing, have been provided to and reviewed by the Food and Drug Administration (^{177}Lu -J591, IND# 11613).

B. ^{177}Lu -PSMA-617 and ^{68}Ga -PSMA-HBED-CC

ABX Advanced Biochemical Compounds, Radeberg, Germany produces both peptides/ligands, PSMA-617 and PSMA-HBED-CC, with PSMA-617 licensed to Endocyte (West Lafayette, LA). Upon purchase and shipment to Weill Cornell Medicine, they will be labeled with either ^{177}Lu or ^{68}Ga with final product being ^{177}Lu -PSMA-617 and ^{68}Ga -PSMA-HBED-CC, respectively. Radionuclide conjugation will be done at the Division of Nuclear Medicine, Department of Radiology, Weill Cornell Medicine.

The material produced are subjected to quality assurance testing as outlined in the Food and Drug Administration "Points to Consider". All production data and supporting documents, together with the results of all quality assurance testing, have been provided to and reviewed by the Food and Drug Administration (^{177}Lu -PSMA-617, IND # 131966 and ^{68}Ga -PSMA-HBED-CC, IND# 124495).

6.2.3 Route of Administration

^{177}Lu -J591, ^{177}Lu -PSMA-617 and ^{68}Ga -PSMA-HBED-CC will be administered intravenously.

6.2.4 Dose levels for ^{177}Lu -J591 + ^{177}Lu -PSMA-617

Subject(s) enrollment will be done as 3+3 study design at each dose level. Initially at least 3 subject(s) will be enrolled in Cohort 1 and will receive ^{177}Lu -PSMA-617 (2 GBq or 54 mCi x2 doses 2 weeks apart) with dose escalation as described above in **Section 4.1 (Table 14)**.

Simultaneously, all subjects will receive in combination a fixed dose of ^{177}Lu -J591 (1.35 GBq/m² or 36.5 mCi/m² capped at BSA of 2) x2 doses, 2 weeks apart. The enrollment ceiling of the dose escalation portion of the study is up to 30 treated study participants (up to five groups, up to 6 at each dose level). Each patient would receive two doses of both investigational agents (^{177}Lu -J591 and ^{177}Lu -PSMA-617) in combination 2 weeks apart. The total dose received by a subject will vary from **4 GBq/m² (108 mCi/m²) to 20 GBq/m² (540 mCi/m²)** for ^{177}Lu -PSMA-617. The total dose received by a subject for ^{177}Lu -J591 will be **2.7 GBq/m² (73 mCi/m²)**, with BSA capped at 2.

6.2.5 Dose levels for ^{68}Ga -PSMA-HBED-CC

All subjected enrolled will receive $5 \pm 2\text{mCi}$ or $185 \pm 74\text{MBq}$ of ^{68}Ga -PSMA-HBED-CC during the screening visit and scan/efficacy visit.

6.2.6 Study drug premedication

No pre-medication is required, but is recommended prior to J591 dosing. Individual subjects may receive pre-medication at the discretion of their treating physician provided that they are not prohibited medications per study. The recommended pre-medication for ^{177}Lu -J591 is a H1 blocker (recommended 25-50 mg diphenhydramine) and acetaminophen (recommended 325-650 mg). No pre-medications will be administered for ^{68}Ga -PSMA-HBED-CC.

6.2.7 Study drug administration

Intravenous access must be well established prior to initiating infusion. At the time of dosing, the IV line will be connected to an infusion container containing the prepared volume of ^{177}Lu -J591, ^{177}Lu -PSMA-617 or ^{68}Ga -PSMA-HBED-CC. ^{177}Lu -J591 will be infused at a rate of no faster than 5 mg/minute. ^{177}Lu -PSMA-617 and ^{68}Ga -PSMA-HBED-CC may be administered as slow IV push.

6.2.8. Monitoring Vital signs pre/post ^{177}Lu -J591 + ^{177}Lu -PSMA-617 and ^{68}Ga -PSMA-HBED-CC

The infusion of ^{177}Lu -J591, ^{177}Lu -PSMA-617 and ^{68}Ga -PSMA-HBED-CC and subsequent monitoring will occur in a facility that is equipped for cardio-pulmonary resuscitation. The dispensed dose will be infused under the supervision of nuclear medicine physician or designee under the supervision of a nuclear medicine physician. Infusion-related reactions (fever, rigors) will be treated with acetaminophen, meperidine and diphenhydramine hydrochloride as clinically appropriate. Other allergic events will be managed as follows: rash, pruritus, urticaria and wheezing will be treated with diphenhydramine hydrochloride, meperidine and/or steroids as clinically appropriate. Anaphylaxis or anaphylactoid signs or symptoms will be treated with steroids and/or epinephrine as clinically indicated. Vital signs will be monitored during the infusion. Systolic and diastolic blood pressure (mm Hg), temperature, pulse rate (beats/minute), and respiratory rate (breaths/minute), will be recorded with the patient in sitting position. Any

clinically significant change in the vital signs will be recorded as AEs. Serial vital signs including temperature, BP, and heart rate will be monitored within 30 minutes before the infusion, within 30 minutes and at 60 minutes (± 10 minutes) [additionally, at 90 ± 10 minutes and 120 ± 10 minutes for ^{177}Lu -J591 + ^{177}Lu -PSMA-617] after the infusion. If any subject has any adverse reaction at 60 minutes for ^{68}Ga -PSMA-HBED-CC and at 120 minutes for ^{177}Lu -J591 + ^{177}Lu -PSMA-617, they will stay longer until it is resolved.

6.2.9. Imaging Plan

A. ^{68}Ga -PSMA-HBED-CC PET/CT Scan

Patient preparation should be according to the policies and procedures of the local imaging site (CBIC). The patient does not need to be fasting for either the infusion or the scans. The use of intravenous or oral contrast will not be permitted. Specifications for acquiring the ^{68}Ga -PSMA-HBED-CC PET/CT scans will be provided in study specific documentation by the study chair or the co-investigators from the Division of Nuclear Medicine. PET/CT should be obtained during the screening visit as well as at the end of study visit (efficacy/scan visit). The images are acquired between 1 and 3 hours after the ^{68}Ga -PSMA-HBED-CC infusion. Image acquisition will be from vertex of skull to mid thighs.

B. Lutetium-177 Planar/SPECT imaging

Patient preparation should be according to the policies and procedures of the local imaging site. The patient does not need to be fasting for either the infusion or the scans. The use of intravenous or oral contrast will not be permitted. Specifications for acquiring the ^{177}Lu -PSMA-617 planar/SPECT images will be provided in study specific documentation by the study chair or the co-investigators from the Division of Nuclear Medicine. Planar/SPECT images should be obtained during the Imaging Visit (Day 8 ± 1) on all subjects after the ^{177}Lu -J591 + ^{177}Lu -PSMA-617 infusion. Image acquisition will be from vertex of skull to mid thighs. Optional images will be performed on selected consenting subjects between initial Treatment Visit (between D1 - D4) and prior to Treatment Visit 2 (Day 15 ± 1).

6.2.10 Managing toxicity

NCI CTCAE version 4.0 is used to grade all adverse events.

- Grade ≥ 2 thrombocytopenia or neutropenia within 24 hours of the second dose of ^{177}Lu -J591 + ^{177}Lu -PSMA-617 (Treatment Visit #2) requires a subject's treatment to be held until the toxicity has resolved to least grade 1. If the toxicity has not resolved after 2 weeks of monitoring, the subject's ^{177}Lu -J591 + ^{177}Lu -PSMA-617 treatment will be permanently discontinued and will be termed dose-limiting toxicity.

Dose-limiting toxicity (DLT) is defined as:

- Grade 4 hematologic toxicity that is deemed at least possibly related to ^{177}Lu -J591 and/or ^{177}Lu -PSMA-617 will be termed dose-limiting toxicity
- Any grade > 2 non-hematologic toxicity deemed to be at least possibly related to ^{177}Lu -J591 and/or ^{177}Lu -PSMA-617 will require a subject's ^{177}Lu -J591 + ^{177}Lu -PSMA-617 treatment to be permanently discontinued and will be termed dose-limiting toxicity.
 - A 1-grade increase in a pre-existing from grade 2 to grade 3 will only be considered a DLT if probably or definitely related to study drug

Maximum Tolerated Dose (MTD) is defined as:

- The dose that produces an “acceptable” level of toxicity or that, if exceeded, would put subjects at “unacceptable” risk for toxicity. Definition of the MTD usually relies on the sample, as MTD is defined as the dose level at which no more than two patients out of six experienced dose-limiting toxicity (DLT).

Note: Toxicities as described above will be considered DLT if they are at least possibly related to ^{177}Lu -J591, ^{177}Lu -PSMA-617 or ^{68}Ga -PSMA-HBED-CC as judged by the investigator (see note above re: 1-grade increases in which case only probably/definitely related toxicities will be deemed DLT). Attribution will be reviewed by the study chair and discussed with the medical monitor if there are questions about severity or attribution.

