| | Dose: GBq (mCi) / m ² | Dose: GBq (mCi) |
| Cohort | | |
| -1 | 2.22 (60) | 1.85 (50) |
| 1 | 2.22 (60) | 3.7 (100) |
| 1a | 1.35 (36.5) | 3.7 (100) |
| 2 | 1.35 (36.5) | 5.55 (150) |
| 3 | 1.35 (36.5) | 7.4 (200) |
| 4 | 1.35 (36.5) | 9.25 (250) |

*Note: BSA will be capped at 2 for ¹⁷⁷Lu-J591 dosing.

Rationale for dosing amendment:

Prior studies of ¹⁷⁷Lu- and ⁹⁰Y-J591 have utilized individualize dosing per body surface area (BSA). As a single agent, ¹⁷⁷Lu-J591 when delivered in a 2-dose fractionated regimen is suggested to be dosed at 45 mCi/m² x2 (or 40 mCi/m² x2 with less toxicity and less efficacy). The dose in combination with docetaxel is 40 mCi/m² x2). In the initial version of the protocol, an estimate for fixed dosing based upon prior safe dose levels and average BSA was utilized. One subject in the initial cohort had prolonged myelosuppression and on analysis, had a low BSA. Therefore based upon the wealth of prior safety data with BSA dosing and the wish to primarily assess one rather than 2 dosing variables, the dosing amendment will revert to BSA dosing. In addition, we will cap BSA at 2 m² with the intent of minimizing myelosuppression from the RIT.

4.2 Phase I:

The Phase I portion will use a 3+3 dose-escalation study design, with the planned initial and subsequent cohorts described in Table 14. This study design is well-described and accepted by the clinical and scientific community, so we will not provide complete details here. Briefly, this design is constructed to reduce the chance of escalating the dose when the probability of DLT is high, and increase the chance of escalating the dose when the probability of DLT is low. The MTD is defined as the highest dose level with an observed incidence of DLT in no more than one out of six patients treated at a particular dose level. The dose escalation scheme provides the following probabilities of escalation based on the true chances of DLT at a specific dose level. One can see that the probability of escalation is high if the toxicity risks are low:

| | | | | | | | |
|-------------------------------|-----|-----|-----|-----|-----|-----|-----|
| True Probability of Toxicity: | .05 | .10 | .20 | .30 | .40 | .50 | .60 |
| Probability of Escalation: | .97 | .91 | .71 | .49 | .31 | .17 | .08 |

As there is a reasonably large pool of short- and long-term experience with PSMA-directed ¹⁷⁷Lu, a phase II trial using the MTD to will be launched to obtain preliminary efficacy data.

4.3 Phase II:

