
We will enroll up to 27 subjects in the Phase II trial utilizing a Simon two-stage design (including the 3-6 patients used for establishing the MTD). For the phase II portion, we will define evaluable patients as those who met eligibility requirements, have initiated therapy, and were not removed from the study for non-compliance or withdrawal. Sample size recommendations for the two-stage design are determined according to Simons two-stage minimax design. The first stage will accrue a total of 16 patients (including those who were treated at the MTD in the phase I portion), if 6 or fewer of the first 16 evaluable patients do not experience a 30% decline in PSA, the study will be terminated and declared to have a negative result. If 7 or more patients out of the first 16 evaluable patients experience a 30% decline in PSA, 9 more patients will be accrued in Stage 2 (total sample size of 27). The new regimen will be declared to have activity and be worthy of further testing if 13 or more patients experience a 30% PSA decline among the 27 patients who are part of the phase II trial.

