12. STATISTICAL CONSIDERATIONS

12.1 Phase I Study Design/Endpoints

The phase I portion is a study of subjects with documented progressive metastatic CRPC with the primary endpoint of determination of MTD (or recommended phase II dose). In general, if there are sufficient numbers of subjects, descriptive statistics (e.g., number of observations, means, standard deviations, medians, and ranges) will be used to summarize data and selected endpoints may be summarized by dosing regimen. Otherwise, subject listings will be provided. No formal hypothesis testing is planned.

The dose-escalation schedule (using 3+3 modified Fibonacci escalation), definitions of DLT, and determination of MTD are defined above (Section 6.2.10). The design is constructed to reduce the chance of escalating the dose when the probability of DLT is high, and increase the chance of escalating the dose when the probability of DLT is low. The maximum tolerated dose is defined as the highest dose level with an observed incidence of DLT in no more than one out of six patients treated at a particular dose level. The dose escalation scheme provides the following probabilities of escalation based on the true chances of DLT at a specific dose level. One can see that the probability of escalation is high if the toxicity risks are low.

| | | | | | | | |
|------------------------------|------|------|------|------|------|------|------|
| True Probability of Toxicity | 0.05 | 0.10 | 0.20 | 0.30 | 0.40 | 0.50 | 0.60 |
| Probability of Escalation | 0.97 | 0.91 | 0.71 | 0.49 | 0.31 | 0.17 | 0.08 |

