12.5 Analysis of Endpoints

12.5.1 Analysis of Primary Endpoints

The primary endpoint will be the proportion of subjects with DLT from Treatment Visit #1 through End of Study (Efficacy/scan) Visit. The MTD is the highest dose amongst the different dose-level cohorts in this study at which no more than 1 out of 6 subjects in a cohort experience DLT.

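### Section 6.2.10 allows up to 2 of 6 DLTs at the MTD, while Sections 4.2, 12.1 and 12.5.1 allow only 1 of 6, so a cohort ending at exactly 2/6 has no settled status

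*Combined protocol and SAP*

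**What the plan says.** The MTD is defined in four places in the combined protocol and SAP.

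- Section 6.2.10 (Managing toxicity), under its MTD heading: "MTD is defined as the dose level at which no more than two patients out of six experienced" a DLT.
- Section 4.2 (Phase I): "The MTD is defined as the highest dose level with an observed incidence of DLT in no more than one out of six patients".
- Section 12.1 (Phase I Study Design/Endpoints): "highest dose level with an observed incidence of DLT in no more than one out of six patients".
- Section 12.5.1 (Analysis of Primary Endpoints): the highest dose at which "no more than 1 out of 6 subjects in a cohort experience DLT".

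Earlier in that same paragraph of Section 12.1, the reader is referred back to the conflicting section: "definitions of DLT, and determination of MTD are defined above (Section 6.2.10".

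Two later steps depend on the answer. Section 4.2 says that "a phase II trial using the MTD to will be launched to obtain preliminary efficacy data". Section 4.3 fills the first 16 places of the Simon design "including those who were treated at the MTD in the phase I portion".

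**The concern.** One section sets the limit at two of six and three set it at one of six. The statistical section endorses both, one by cross-reference and one by statement, and nothing gives either precedence. Section 6.2.10 is also where DLT itself is defined, so it is the section that investigators will open when a cohort is being judged.

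If a cohort ends at 2/6, that dose can be the MTD under 6.2.10 and is above the MTD under the other three sections. The choice would then be made in an open-label, single-center study after the toxicity results, and possibly PSA results, are known. It would decide two things:

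- whether Phase II patients are treated at a dose that three sections call too toxic;
- which Phase I patients are carried into the Phase II efficacy test.

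**Working it through.** **Inputs.** The 3+3 design, the true DLT rates and the printed escalation probabilities come from Sections 4.2 and 12.1. The dose levels come from the dose-escalation table in Section 4.1. Let p be the true DLT rate at a level.

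**Step 1: reproduce the printed table.** With a limit of one in six, a level is passed on 0/3, or on 1/3 followed by 0/3:

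P(escalate) = (1−p)³ + 3p(1−p)²·(1−p)³ = (1−p)³ + 3p(1−p)⁵

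At p = 0.30: 0.343 + 0.9 × 0.168 = 0.494; the table prints 0.49.

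**Step 2: probability of the disputed result.** A cohort ends at exactly 2/6 on 1/3 followed by 1/3:

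P(2/6) = [3p(1−p)²]² = 9p²(1−p)⁴

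At p = 0.30: 9 × 0.09 × 0.2401 = 0.194.

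**Step 3: what a two-in-six limit would give.** The probability of accepting a level is the sum of steps 1 and 2.

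| True DLT rate | Printed P(escalate) | Limit 1/6 | Limit 2/6 | P(exactly 2/6) |
|---|---|---|---|---|
| 0.05 | 0.97 | 0.973 | 0.992 | 0.018 |
| 0.10 | 0.91 | 0.906 | 0.965 | 0.059 |
| 0.20 | 0.71 | 0.709 | 0.856 | 0.147 |
| 0.30 | 0.49 | 0.494 | 0.689 | 0.194 |
| 0.40 | 0.31 | 0.309 | 0.496 | 0.187 |
| 0.50 | 0.17 | 0.172 | 0.313 | 0.141 |
| 0.60 | 0.08 | 0.082 | 0.165 | 0.083 |

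The one-in-six limit reproduces all seven printed values. The two-in-six limit does not. If expansion after 2/3 is also allowed, it is further off (0.754 at p = 0.30).

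**Step 4: the trial as a whole.** The probability that escalation through cohorts 1a, 2, 3 and 4 stops on a 2/6 cohort is the sum, over cohorts, of (product of earlier P(escalate)) × P(2/6). The documents give no DLT rates for the combination, so the curves below are assumptions.

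| Assumed DLT rates, cohorts 1a / 2 / 3 / 4 | Stop on 2/6, any cohort | Stop on 2/6, cohorts 2–4 only |
|---|---|---|
| 0.05 / 0.05 / 0.05 / 0.05 | 0.070 | 0.070 − 0.018 = 0.052 |
| 0.05 / 0.10 / 0.20 / 0.30 | 0.327 | 0.327 − 0.018 = 0.309 |
| 0.10 / 0.20 / 0.30 / 0.40 | 0.377 | 0.377 − 0.059 = 0.318 |
| 0.20 / 0.30 / 0.40 / 0.50 | 0.366 | 0.366 − 0.147 = 0.219 |

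For the second row, the four terms are 0.018 + 0.973 × 0.059 + 0.973 × 0.906 × 0.147 + 0.973 × 0.906 × 0.709 × 0.194 = 0.327.

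**Step 5: are rates in this range plausible?** Section 6.2.10 counts any grade 4 hematologic toxicity at least possibly related to treatment as a DLT, with no minimum duration. Tables 1 and 11 report 40% grade 4 thrombocytopenia with ¹⁷⁷Lu-J591 alone at 35 + 35 mCi/m². Cohorts 1a to 4 give 36.5 + 36.5 mCi/m² plus ¹⁷⁷Lu-PSMA-617. Taking 0.40 as a flat rate gives 0.187 × (1 + 0.309 + 0.096 + 0.030) ≈ 0.27. The tables do not show the size of that dose group, so this is illustrative only.

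**Step 6: size of the consequence.** For a 2/6 result in cohorts 2 to 4, the rules select doses at least one level apart: 1.85 GBq (50 mCi) per dose, or 2 × 1.85 = 3.7 GBq (100 mCi) cumulative ¹⁷⁷Lu-PSMA-617. For cohort 1a the dose table has no lower level at the same ¹⁷⁷Lu-J591 dose, so no such gap is computed. Six patients from the disputed cohort are 6/16 = 38% of stage 1.

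**The case against.** The strongest reply is that the intended rule is easy to infer. One in six appears three times, including in both statistical sections that define and analyse the endpoint, and the printed probabilities fit nothing else. The sentence in 6.2.10 sits in a toxicity-management section and reads partly as general background. This stands as evidence of which sentence is wrong. It does not remove an operative definition that Section 12.1 expressly cites.

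Escalation is also unaffected: under the 3+3 table a 2/6 cohort stops escalation either way, so the dispute is confined to which dose is then called the MTD. That is correct, but this label is the Phase I primary endpoint and sets the Phase II dose.

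The stage 1 effect is a swap. Under the one-in-six rule, the three to six patients at the lower level would be pooled instead. That is fair; the 38% describes whose data are used, not patients gained or lost.

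Section 6.2.10 also describes the MTD as a dose beyond which risk becomes unacceptable, which hints at an upper bound. The hint is one of two alternatives joined by *or*, and it does not make the six-patient criterion select a single highest level.

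Finally, the DSMB is notified after each cohort and before Phase II. Notification makes the step visible but supplies no rule for deciding it.

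**Conclusion.** The concern holds. The protocol gives two incompatible thresholds for its Phase I primary endpoint, and 6.2.10 is the one in error. The conflict bites only at exactly 2/6. That result has probability 2% to 19% per cohort for true DLT rates of 0.05 to 0.60, and is most likely near 0.30 to 0.40. Across the trial the probability is 7% to 38%, or 5% to 32% for cohorts 2 to 4, where the rules differ by at least one dose level.

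The per-cohort figures assume the standard 3+3 path; the trial-level figures also rest on assumed DLT curves. Only the 1/3-then-1/3 route to 2/6 is counted. The conflict itself rests on the text alone. It should be resolved before any MTD is declared, because it bears on patient safety as well as on who enters the efficacy analysis.

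**What to change.** In the last sentence of the MTD definition in Section 6.2.10, insert *highest* before *dose level* and change *two patients* to *one patient*. The section then agrees with 4.2, 12.1 and 12.5.1, and the cross-reference in 12.1 becomes correct as it stands.

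The cost is a one-sentence amendment, with no added patients. The escalation tables in 4.2 and 12.1 stay as printed; they would need recomputing only if the sponsor wanted 2/6 to permit escalation as well.

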12.2. Phase II Study Design/Endpoints

We will enroll up to 27 subjects into the Phase II portion (including the 3-6 used for establishing the MTD). We will define evaluable patients as patients who met eligibility requirements, have initiated therapy, and were not removed from the study for non-compliance or patient withdrawal.

Sample size recommendations for the two-stage design are determined according to Simon's two-stage minimax design. We project a 30% PSA decline proportion of 35%, below which the regimen will be unacceptable and a 30% PSA decline proportion of 60%, above which the regimen will be considered worthy of further exploration. The null hypothesis that the 30% PSA decline proportion is less than or equal to 35% will be tested against the alternative hypothesis that the 30% PSA decline proportion is greater than or equal to 60%.

The sample size computations were performed assuming a 0.10 one-sided level of significance and 90% power assuming a historical control value for PSA decline of 35% and the alternative

hypothesis of 60%. If 6 or fewer of the first 16 evaluable patients do not experience a 30% decline in PSA (stage 1), the study will be terminated and declared to have a negative result. If 7 or more patients out of the first 16 evaluable patients experience a 30% decline in PSA, ongoing accrual will proceed to the target sample size of 27 patients (stage 2). The new regimen will be declared active in this patient population and worthy of further testing if 13 or more patients experience a 30% PSA decline among the 27 patients entered. This two-stage design yields a 0.90 probability of a positive result if the true 30% PSA decline proportion is 60%. It yields a 0.90 probability of a negative result if the true 30% PSA decline proportion is 35%. An exact 95% binomial confidence interval will be constructed for the proportion of patients with PSA decline.

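### Section 6.2.10 sets the MTD limit at two DLTs in six patients, against one in six in Sections 4.2, 12.1 and 12.5.1; Section 6.2.10 is the text to correct

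*Combined protocol and SAP*

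**What the plan says.** Four places in the combined protocol and SAP give a numerical limit for the MTD.

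- Section 6.2.10 (Managing toxicity): "MTD is defined as the dose level at which no more than two patients out of six" had a DLT.
- Section 4.2 (Phase I): "The MTD is defined as the highest dose level with an observed incidence of DLT in no more than one out of six patients".
- Section 12.1 (Phase I Study Design/Endpoints): the highest level with observed "DLT in no more than one out of six patients treated at a particular dose level".
- Section 12.5.1 (Analysis of Primary Endpoints): the highest dose at which "no more than 1 out of 6 subjects in a cohort experience DLT".

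Section 12.1 also says that the escalation schedule, the DLT definitions and "determination of MTD are defined above (Section 6.2.10"), and two sentences later it gives the one-in-six limit itself. Sections 4.2 and 12.1 print the same table of escalation probabilities. Section 4.2 relies on the 3+3 being well known, "so we will not provide complete details here", so the table is the fullest numerical account of the rule.

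**The concern.** Determining the MTD is a Phase I primary objective, and the MTD is the dose at which Phase II is run. The statistical section sends the reader to Section 6.2.10 for the rule, and Section 6.2.10 has the one limit that disagrees with the rest. The two limits give opposite decisions when a level ends at exactly 2/6, an observed DLT rate of 33% (exact 95% CI 4% to 78%), against 17% (0.4% to 64%) at 1/6.

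That outcome is not remote. Section 6.2.10 counts any grade 4 hematologic toxicity at least possibly related to treatment as a DLT, with no duration qualifier. The cumulative antibody dose is now 73 mCi/m². The background tables report grade 4 thrombocytopenia in 40% at a fractionated 70 mCi/m² and 50% at 80 mCi/m² of single-agent antibody. These figures illustrate the risk and do not forecast it: the cohorts were small, no grade 4 neutropenia was seen at the fractionated 70 mCi/m², BSA is now capped at 2, and the docetaxel combination study reported grade 4 thrombocytopenia in 13% and grade 4 neutropenia in 33%.

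**Working it through.** **Inputs.** True DLT probabilities p and printed escalation probabilities come from the table in Sections 4.2 and 12.1. The limits come from the sections quoted above. Write q = 1 − p. In a cohort of three, P(0/3) = q³, P(1/3) = 3pq² and P(2/3) = 3p²q.

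**Step 1: reproduce the printed table.** Under one in six, a level passes on 0/3, or on 1/3 followed by 0/3:

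P(pass) = q³ + 3pq² · q³.

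At p = 0.30: 0.343 + 0.441 × 0.343 = 0.494. The plan prints 0.49.

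**Step 2: apply two in six.** No section writes out a 3+3 with this limit, so three variants are shown.

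- A: 1/3 expands, at most 2/6 passes, 2/3 stops: q³ + 3pq²(q³ + 3pq²). At p = 0.30: 0.343 + 0.441 × 0.784 = 0.689.
- B: as A, but 2/3 also expands and passes if the next three have no DLT: add 3p²q · q³. At p = 0.30: 0.689 + 0.189 × 0.343 = 0.754.
- C: six patients treated outright, at most two DLTs: P(X ≤ 2), X binomial(6, p). At p = 0.30: 0.744.

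| True DLT rate | Printed | One in six | Two in six, A | Two in six, B | Two in six, C |
|---|---|---|---|---|---|
| 0.05 | 0.97 | 0.973 | 0.992 | 0.998 | 0.998 |
| 0.10 | 0.91 | 0.906 | 0.965 | 0.985 | 0.984 |
| 0.20 | 0.71 | 0.709 | 0.856 | 0.905 | 0.901 |
| 0.30 | 0.49 | 0.494 | 0.689 | 0.754 | 0.744 |
| 0.40 | 0.31 | 0.309 | 0.496 | 0.558 | 0.544 |
| 0.50 | 0.17 | 0.172 | 0.313 | 0.359 | 0.344 |
| 0.60 | 0.08 | 0.082 | 0.165 | 0.193 | 0.179 |

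The one-in-six rule agrees with the printed row at all seven points to two decimals. Variants A, B and C agree at none.

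**Step 3: how often the two limits disagree.** In the sequential 3+3 where 2/3 stops, a level ends at exactly 2/6 with probability (3pq²)²: 0.384² = 0.147 at p = 0.20, 0.441² = 0.194 at 0.30, 0.432² = 0.187 at 0.40 and 0.375² = 0.141 at 0.50. This is the gap between variant A and the one-in-six column.

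**The case against.** The strongest reply is that the plan already points to one rule with a single stray sentence. One in six stands in the design section, the statistical section and the primary-endpoint analysis. The Section 6.2.10 definition is loosely worded. Section 14 has the DSMB notified before each escalation and before Phase II. Most of this stands, and it limits the consequence. A reader might infer that anyone following the Section 12.1 cross-reference would accept a dose after 2/6. The documents do not support that, because the same paragraph goes on to state one in six and the reader meets both limits together. What remains is that neither the cross-reference nor the DSMB provision says which limit governs.

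A second reply is that the table gives probabilities of escalation, whereas Section 6.2.10 defines the MTD. That is correct. The table corroborates one in six; the text of Sections 4.2, 12.1 and 12.5.1 sets it. The two-in-six figures also depend on an unstated expansion rule, which is why a range is given.

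A reader might further infer that the plan lets an MTD rest on three patients and must be changed to require six, since Section 4.3 has "including the 3-6 patients used for establishing the MTD" and Section 12.2 has "including the 3-6 used for establishing the MTD". The documents do not support treating this as an error. Both phrases are parentheses about which Phase I patients count toward Phase II. The MTD definitions use a denominator of six, so expansion to six is a fair reading. Requiring six in every case would also be a design change with a price. At a level that would otherwise close on 0/3, the chance of acceptance at a true 20% DLT rate would fall from 0.71 to 0.66 (q⁶ + 6pq⁵ = 0.655), and waiting out the DLT window could add about 12 weeks.

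**Conclusion.** The inconsistency is real, is in current operative text, and concerns the threshold that fixes the Phase II dose. Section 6.2.10 is the outlier: three sections and all seven table entries agree on one in six. If two in six were applied, the chance that a level with a true 30% DLT rate passes would rise from 0.49 to about 0.69 to 0.75, and at 40% from 0.31 to about 0.50 to 0.56. These figures assume independent patients with a common DLT probability at a level, and they depend on the variant chosen. The conclusion about which text is wrong does not depend on the variant. The point stops there: it does not establish that a 2/6 dose would be carried forward, or that the number of patients at the MTD is deficient.

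**What to change.** In Section 6.2.10, change the limit in the MTD sentence from two patients out of six to one patient out of six. The cross-reference in Section 12.1 then leads to the same rule that Section 12.1 states. The escalation table, cohort sizes and Phase II design stay as they are. The cost is a wording correction in one sentence.

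As an optional clarification only, the sponsor could say whether a level that closes on 0/3, such as the top cohort, is expanded to six before Phase II accrual continues. That is a trade-off for the sponsor to weigh. If it is adopted, the text would need to define which patients are evaluable for DLT, because the plan defines evaluability for toxicity (Section 12.6.1) and for response (Section 12.6.2) but not for DLT.
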